**Table 9 Sensitivity of Sample Size to Standardized Effect Size for PSPs**

d	Target Power	Actual Power	N1	N1'	N2	N2'	N	N'
0.44	0.8	0.8	62	73	124	146	186	219
0.44	0.85	0.85	71	84	142	168	213	252
0.44	0.9	0.9	83	98	166	196	249	294
0.45	0.8	0.8	59	70	118	139	177	209
0.45	0.85	0.85	68	80	136	160	204	240
0.45	0.9	0.9	79	93	158	186	237	279
0.46	0.8	0.8	57	68	114	135	171	203
0.46	0.85	0.85	65	77	130	153	195	230
0.46	0.9	0.9	76	90	152	179	228	269
0.47	0.8	0.8	54	64	108	128	162	192

d	Target Power	Actual Power	N1	N1'	N2	N2'	N	N'
0.47	0.85	0.85	62	73	124	146	186	219
0.47	0.9	0.9	72	85	144	170	216	255
0.48	0.8	0.8	52	62	104	123	156	185
0.48	0.85	0.86	60	71	120	142	180	213
0.48	0.9	0.9	70	83	140	165	210	248
0.49	0.8	0.8	50	59	100	118	150	177
0.49	0.85	0.85	57	68	114	135	171	203
0.49	0.9	0.9	67	79	134	158	201	237
0.5	0.8	0.8	48	57	96	113	144	170
0.5	0.85	0.85	55	65	110	130	165	195
0.5	0.9	0.9	64	76	128	151	192	227
0.51	0.8	0.8	46	55	92	109	138	164
0.51	0.85	0.85	53	63	106	125	159	188
0.51	0.9	0.9	62	73	124	146	186	219

**Figure 7 Relationship between Minimum Sample Size Required for RI Arm and the Assumed Standardized Effect Size for PSPs**

### 5.3. Essential Analysis

The primary endpoint in terms of feasibility is SSPs' mean FIM score at Month 13 under Dynamic Implementation (DI) arm and Routine Implementation (RI) arm respectively, and the difference of their mean FIM scores between arms. For FIM of SSPs and the difference between arms, descriptive statistics including 95% confidence intervals will be displayed for these estimates. Mean FIM scores will be compared between the two implementation arms to test if the observed difference is statistically significant. In

addition, distribution of FIM items scores will also be compared. P-values will be reported for these comparisons.

To address the potential intra-cluster correlation effect due to the cluster randomization design, classical methods such as mixed effects linear regression model or Generalized Estimating Equations will be utilized. Besides the analysis on the subject level, the stratification analysis will be performed at the site level to evaluate the impact of the capacity of sites (high volume vs low volume) in responses to two implementation strategies imposed on SSPs. Exploratory analysis will be undertaken to assess the variability of responses by other factors such as subset of implementation strategies.

In addition to summary of mean FIM scores of SSPs at different timepoints, the change in mean FIM scores from baseline will be analyzed at the designated timepoints. For the specific Telehealth implementation strategy on SSPs, the subgroup analysis on FIM scores including change from baseline will be conducted.

The FIM scores of PSPs will be summarized in the same way as those of SSPs. In addition, subgroup analysis on PSPs will include, but not limited to, factors such as demographic, baseline characteristics, study arm, clinic characteristics and APRETUDE initiation method. To address the potential differential dropout rates of PSPs between arms, appropriate imputation methods will be undertaken to handle missing data of different type.

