#### 3.1. Study Design

This is a Phase 4, randomized, open-label, two-arm study evaluating the impact of two implementation strategy conditions – dynamic implementation and routine implementation – on the delivery of CAB PrEP in low and high-volume PrEP sites in the U.S. for MSM and Transgender men  $\geq 18$  years of age. MSM and transgender men who tested HIV-1 negative at the sites prior to initiation of CAB PrEP (Section 3.2.1) will be enrolled. Approximately eighteen clinics – about 9 high and about 9 low volume – will be randomized 2:1 to either dynamic implementation or routine implementation. This study is being conducted following FDA approval and commercial availability of CAB PrEP in the U.S.

Eligible and consenting PSPs will be followed for 12 calendar months from the time of enrollment and receipt of the first administration of CAB tablets for PrEP oral lead in or APRETUDE (for direct to injection PSPs). The study includes a screening period of up to 90 days to allow sufficient time for any benefit verification checks to be completed, as required. PSPs will be initiated on CAB PrEP as soon as their eligibility is confirmed. The screening period is followed by a 11-month or 12-month administration period of CAB PrEP depending on whether an optional 1-month oral lead-in of CAB tablets for PrEP is administered, followed by APRETUDE IM injections every two months after the one-time loading dose (i.e., first 2 IM doses 1 month apart and 2 months apart thereafter). All PSPs will receive a total of 7 APRETUDE IM injections, with the last IM injection visit being their last study visit. After 11-month (direct to injection) or 12-month (with OLI) treatment period, PSPs will complete the study and will be offered PrEP regimen as per site standard of care. When PSPs complete their M12/M13 assessments, irrespective of missed injections, they will be a completer. Consenting SSPs at the site will participate in study quantitative and qualitative study assessments to evaluate the impact of the two implementation strategy conditions on the feasibility of delivering APRETUDE. When SSPs completes their M13 study assessments, they will be a completer. The end of study is defined when the last PSP and SSP have completed their implementation science assessments. For a detailed Schedule of Activities (SoA) refer to [ANNEX 1](#) and [ANNEX 2](#). CAB PrEP dosing information can be found in the prescribing information for CAB PrEP.

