**Figure 1 Study Design Schematic****3.2. Study Population**

Approximately 220 PSPs will be enrolled. We aim for at least 50% of the enrolled PSPs to be Black or Latino. Of the total PSPs enrolled, we aim for at least 2-4% to be TGM. The number of SSPs will vary by site and approximately 5 per site will be included.

During the screening period, PSPs who enroll into the study will complete informed consent and confirmation of inclusion and exclusion criteria will be conducted. Each PSP being screened for study enrollment evaluation will be assigned a PSP number at the screening visit (refer to the SRM for details). Completion of study assessments will occur prior to receipt of Dose 1(D1) of intramuscular (IM) injections.

SSPs will be selected in advance of the investigator meeting and will be enrolled and assigned an SSP number (refer to the SRM for details) around the time of the site initiation visit, prior to the site's first subject visit.

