## 4. Implementation Research Methods

### 4.1. Study Arms Overview

The two study arms are routine implementation and dynamic implementation. Clinics will be randomized to the two study arms in a 2:1 distribution, whereby about 12 clinics will be in the dynamic implementation arm and about 6 clinics will be in the routine implementation arm (Note: Number of clinics may vary depending on recruitment). Clinics receiving routine implementation will receive standard provider and patient toolkits that will be available when CAB PrEP is commercially available. Clinics receiving dynamic implementation will receive enhanced toolkits, a digital health end to end implementation strategy, and implementation facilitation. An overview of the RI and DI implementation strategies are outlined in [Table 1](#) and [Table 2](#) in terms of six dimensions as recommended by Proctor and colleagues [[Proctor](#), 2013]: actor, the action, action targets, dose, implementation outcomes addressed, and theoretical justification.

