### 5.1. Statistical Hypotheses

The primary hypothesis on the quantitative aspects of this study is that there is a difference between the dynamic implementation (DI) strategy and the routine implementation (RI) strategy in terms of staff study participants' (SSPs) mean FIM score at Month 13, i.e.,

$$H_{10} : \mu(\text{DI}) = \mu(\text{RI}) \text{ vs } H_{11} : \mu(\text{DI}) \neq \mu(\text{RI}),$$

and the secondary hypothesis is that there is a difference between the dynamic implementation (DI) strategy and the routine implementation (RI) strategy in terms of patient study participants' (PSPs) mean FIM score at Month 13, i.e.,

$$H_{20} : \mu(\text{DI}) = \mu(\text{RI}) \text{ vs } H_{21} : \mu(\text{DI}) \neq \mu(\text{RI}).$$

The two-way ANOVA will be used to test each of the above hypothesis with clinic volume as the stratification factor, where no multiplicity adjustment is planned.

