### Sample Size of SSPs:

For SSPs, its size consideration consists of two parts: one is based on practical considerations in terms of feasibility of enrolling an adequate number of sites on each implementation strategy with the desire to have interventions tested across two types of study sites (high vs low), and the other is to enroll an adequate number of SSPs in each site to achieve the targeted power to detect the various differences between two arms (DI vs RI) in term of their mean FIM score with the cap 90 on the number of SSPs to be enrolled.

With the cap 90 on the number of SSPs and the allocation of SSPs between DI arm and RI arm being 2:1, the absolute value of  $d$  will range approximately from 0.63 to 0.73 if the study power changes from 0.80 to 0.90, as shown in [Table 4](#) below, where [Figure 4](#) illustrates the relationship between  $d>0$  and the study power.

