**Figure 4 Relationship between Standardized Effect Size and Study Power for SSPs**

Results from study CUSTOMIZE (209493) have shown that the estimated mean score of FIM for SSPs was 4.46 with standard deviation (SD) 0.59 at Month 12. Assuming these results remain valid in our RI arm (N1=30) at Month 13 when 90 SSPs are enrolled in DI and RI with ratio 2:1, to achieve 80% power, the mean score  $\mu(\text{DI})$  of FIM at Month 13 for DI arm should be at least 4.83 if DI arm behaves better than RI arm, or at most 4.09 if vice versa, as the absolute mean difference  $|\mu(\text{DI}) - \mu(\text{RI})|$  will be  $0.37 \approx 0.59 * 0.63$  ( $=\sigma^*d$ ). The mean FIM score of DI arm at Month 13 will be at most 4.06 if  $\mu(\text{DI}) < \mu(\text{RI})$  or at least 4.86 if  $\mu(\text{DI}) > \mu(\text{RI})$  to have 85% power. The other scenarios of  $\mu(\text{DI})$  are summarized for the range of detectable standardized effect size and the corresponding powers in [Table 5](#).

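### Sections 5.1 and 5.3 leave the primary test open and allow GEE on about 18 clinics with no small-sample safeguard; fitted in its usual form, GEE would reject about 10-11% instead of 5%

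*Protocol*

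**What the plan says.** Section 3.1 makes the clinic the unit of allocation: about eighteen clinics, about half high and half low volume, "will be randomized 2:1 to either dynamic implementation or routine implementation". Section 4.1 expects that "about 12 clinics will be in the dynamic implementation arm and about 6 clinics will be in the routine implementation arm", and notes that the count may change with recruitment. Section 3.2 says of staff participants (SSPs) that "approximately 5 per site will be included", and Section 5.2 plans "with the cap 90 on the number of SSPs".

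The primary hypothesis in Section 5.1 is that "there is a difference between the dynamic implementation (DI) strategy and the routine implementation (RI) strategy" in mean SSP FIM score at Month 13. The same section assigns the test to a two-way ANOVA with clinic volume as the stratification factor and does not mention clinic.

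Section 5.3 describes the same comparison with 95% confidence intervals and p-values. It then says that, because of the cluster randomization, "classical methods such as mixed effects linear regression model or Generalized Estimating Equations will be utilized". The Abstract repeats this. Neither place chooses between the two methods or states a variance estimator, a reference distribution or degrees of freedom. The opening of Section 5 leaves technical detail to the SAP, which is to be final before any interim or final database lock.

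**The concern.** The usual GEE standard error is justified as the number of clusters grows. With few clusters, the squared residuals in the sandwich variance are too small on average, and the z reference ignores how imprecisely that variance is estimated. Both faults push towards rejection. Here the RI arm has about 6 clusters.

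The text therefore presents as interchangeable two methods that do not behave alike in this design, while Section 5.1 names a third. An analyst could follow Section 5.3 exactly, fit GEE with default settings, and report a primary p-value and confidence interval with about twice the nominal error rate. That affects the trial's only primary comparison.

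**Working it through.** **Inputs from the protocol.** 12 DI and 6 RI clinics (Section 4.1); about 5 SSPs per clinic, 90 in all, 30 RI and 60 DI (Sections 3.2 and 5.2); a two-sided question (Section 5.1).

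**Assumptions.** Two-sided alpha 0.05, which is not stated as a number but matches the 95% intervals and reproduces Table 4. ICC from 0 to 0.4, because none is given. High and low volume clinics evenly split within each arm.

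**The plan's own figure first.** Section 5.2 says that the detectable |d| "will range approximately from 0.63 to 0.73 if the study power changes from 0.80 to 0.90". The noncentrality is d × √(30 × 60 / 90) = d × √20. For d = 0.63 this is 0.63 × 4.472 = 2.817, giving power 0.796 (t, 88 df) or 0.804 (normal), against the stated 0.80. For d = 0.73 it is 3.265, giving 0.898 (t), against 0.90. Table 4 reproduces with two-sided alpha 0.05 and no ICC.

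**Why the sandwich variance is too small.** With equal clinic sizes and covariates that vary only between clinics, exchangeable GEE with identity link equals least squares on clinic means. Let σ² be the variance of a clinic mean.
- True variance of the arm difference: σ²(1/12 + 1/6) = 0.250σ².
- Expected sandwich variance, arm only: σ²[(11/12)/12 + (5/6)/6] = σ²(11/144 + 20/144) = 0.215σ², or 86% of the truth.
- With volume added, each leverage rises by 1/18, to 5/36 (DI) and 2/9 (RI). The expected variance is σ²[(31/36)/12 + (7/9)/6] = 0.201σ², or 81% of the truth.

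The ICC enters only through σ², which cancels. This is why the inflation does not depend on it. In simulation with volume in the model, the mean standard error is about 12% too small.

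**Rejection rate under no effect** (simulated on clinic means; nominal 5%; volume in the model unless stated):

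| Analysis | Rejection rate |
|---|---|
| GEE, uncorrected sandwich, z, arm and volume | 10.5-10.9%, ICC 0 to 0.4 |
| Same, arm only | 9.5-9.8%, ICC 0 to 0.4 |
| REML mixed model, z | 4.4% (ICC 0), 5.5% (0.05), 6.1% (0.1), 6.7% (0.2), 6.9% (0.4) |
| Two-way ANOVA ignoring clinic | 7.4% (ICC 0.05), 9.8% (0.1), 14.9% (0.2) |
| Clinic means, t on 15 df | 5.0% |
| GEE, Kauermann-Carroll variance, t on 15 df | 5.7-5.8% |
| GEE, Mancl-DeRouen variance, t on 15 df | 3.8-3.9% |

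**Robustness.** GEE fits to individual data gave 9.0-10.7% with equal clinics of 5. With clinic sizes of 2 to 8 they gave 10.5-12.9%. Those sizes are illustrative and each setting had only 1,500 fits, so these rates are rough. A bounded FIM-like score (mean about 4.42, SD about 0.58, near the "4.46 with standard deviation (SD) 0.59 at Month 12" that Section 5.2 cites) gave 9.5-10.8%.

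**The case against.** The strongest reply is that the protocol does not fix the faulty procedure. GEE follows the words for such as, and the mixed model comes first. Doubling the error needs three choices that the text never makes: GEE over the mixed model, an uncorrected variance, and a z reference. Variance corrections and degrees of freedom are normal SAP content, Section 5 defers technical detail there, and the SAP is not shown. All of this stands, and it sets the limit of the point. A reader might infer that the primary test will run at about 10%, or that the plan as a whole lacks a correction; the documents support neither. What remains is that the protocol offers GEE for about 18 clusters without any condition.

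A reader might also infer that a mixed model with large-sample tests shares the fault. That is not so in general. REML holds the clinic variance at or above zero, which makes the test slightly conservative at ICC 0, and it is only moderately liberal at high ICC. A between-clinic variance with z gives about 6.7-7.0%, but that is the upper end of the mixed-model range, not its typical value.

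Finally, Section 5.1 names an ANOVA, so GEE may not be the primary test at all. This does not rescue the plan. An ANOVA that ignores clinic also loses its level once there is any material ICC, and the two sections still disagree about which method carries the hypothesis.

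**Conclusion.** The point holds as a conditional one. Section 5.3 and the Abstract permit, for the only primary comparison, a method that in its usual form rejects about 10-11% of the time under no effect (9.5-10% with arm only). That is about twice nominal and does not depend on the unknown ICC. It assumes two-sided alpha 0.05, 12 and 6 clinics, and about 5 SSPs each; unequal clinic sizes tend to make it worse. It is a risk of one permitted option, not a predicted result. The first-named mixed model is much closer to nominal, and the SAP may already contain a safeguard. Section 5.1 adds a second unsafe reading if its ANOVA ignores clinic, with an error rate that rises with the ICC. Because the two sections name different methods for one hypothesis, they should be settled together.

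**What to change.** Amend Sections 5.1 and 5.3 together, with the Abstract, so that they name one primary test. That test should be a linear mixed model for SSP FIM at Month 13 with a clinic random effect, arm and volume stratum, using Kenward-Roger or between-clinic degrees of freedom. The between-clinic degrees of freedom are the number of clinics minus 3, so 18 - 3 = 15 as planned; write the rule rather than the number, since the clinic count may change. A clinic-mean analysis with t on those degrees of freedom is equivalent when clinics are of equal size. Remove the two-way ANOVA as the test, or state that it is done on clinic means. Keep GEE only with a bias-corrected sandwich variance and a t reference. Of the two corrections checked, Kauermann-Carroll is slightly liberal and Mancl-DeRouen slightly conservative.

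The cost is a few sentences and no new data. Confidence intervals become wider. For the same standard error, the multiplier rises from 1.960 to 2.131 at 15 df, about 9% (2.131 / 1.960 = 1.087). The widening is larger against uncorrected GEE, whose standard error is too small to begin with.

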## 5.4. Secondary Analysis

Key secondary outcomes include

- Acceptability and feasibility of telehealth delivery: The mean Acceptability of Intervention Measure (AIM) score and Feasibility of Intervention Measure (FIM) score for SSPs and PSPs will be calculated. The scores will be calculated at Baseline, Month 5 and Month 13 for SSPs, and at Baseline, Month 7 (OLI)/Month 6(DTI), and Month 13(OLI)/Month 12(DTI) for PSPs. Change from Baseline of mean score in the AIM and FIM scores at the respective time points from SSPs and PSPs will also be calculated. Descriptive statistics will be used including 95% confidence intervals. Exploratory analyses will be undertaken to assess the variability of responses by factors including but not limited to clinic characteristics, SSP role and study arm.

Additional analyses will assess SSPs and PSPs responses to acceptability and feasibility questions posed in the IS questionnaires. The finalization of the questionnaires will inform the latter analyses.

Other secondary outcomes to evaluate include:

- Change from baseline in SSPs' FIM score of RI and DI for APRETUDE administration over time

- SSPs perceptions of facilitators and barriers to RI and DI and overall implementation of PrEP into routine care assessed over time
- PSPs mean FIM and AIM score as well as ISQ responses for APRETUDE over time
- Change from baseline in PSPs' AIM score and FIM score as well as ISQ responses for APRETUDE over time
- PSPs perception of facilitators and barriers to feasibility and acceptability of APRETUDE over time'
- SSPs' mean AIM score and ISQ responses for RI and DI for APRETUDE administration over time
- Change from baseline in SSPs' AIM score and ISQ responses for RI and DI for APRETUDE administration over time
- PSPs' mean AIM score and ISQ responses by implementation strategy over time
- Change from baseline in PSPs' mean AIM score and ISQ responses by implementation strategy over time
- Proportion of SSPs and PSPs that agree or completely agree on the ISQ that each implementation strategy is fit for use over time
- SSPs and PSPs perceptions of utility of implementation strategies and PSPs perceptions of facilitators and barriers to acceptability of RI and DI over time
- Proportion of injections occurring within target window from target date ( $\pm$  7 days for Injection dose 2 and  $\pm$  7 days of target date for subsequent injections) over time
- Proportion of PSPs completing target number of injections through M13
- PSPs and SSPs perception of barriers and facilitators to fidelity to injections window over time
- Proportion of site staff who administer Sexual Health Assessment for APRETUDE over time
- Proportion of eligible PSPs for which Sexual Health Assessment for APRETUDE are administered over time
- Proportion of MSM and TGM who take the Sexual Health Assessment over time
- Proportion of MSM & TGM who report having had sex in the last 6 months on Sexual Health Assessment over time
- Proportion of MSM & TGM who expressed interest in PrEP or never heard of PrEP out of those who report having had sex in the last 6 months over time
- Proportion of PSPs who initiate APRETUDE after taking the Sexual Health Assessment over time
- SSPs and PSPs perceptions of Sexual Health Assessment over time

- Summarize components adapted and changes made using FRAME-IS at pre-implementation and over time
- SSPs and PSPs perceptions of barriers and facilitators over time
- Proportion of PSPs with history of PrEP use that complete the Sexual Health Assessment and ISQ and start APRETUDE over time
- PSPs reasons for choosing APRETUDE, including switching, as assessed by SSIs and ISQ
- SSIs, FRAME-IS and facilitation calls assessed qualitatively with SSPs and SSIs with PSPs over time

In general, descriptive summaries will include number of subjects, means, standard deviations, median, first and third quartiles, as well as the minimum and maximum values for continuous outcomes; and counts and proportions are presented for categorical measures for outcomes in endpoints above. Unless otherwise stated, a 95% confidence interval (CI) will be provided for means and proportions.

Analyses of the implementation outcomes for SSPs and PSPs will use standardized measures, such as the FIM and AIM, as well as items from the ISQ that measure these outcomes using different terminology ([Table 10](#)) [[Proctor, 2011](#), [Weiner, 2017](#), [Aarons, 2015](#)]. SSPs analyses will also be conducted by factors including but not limited to study arm, staff role, and clinic characteristics. PSPs analyses will also be conducted by factors including but not limited to study arm, clinic characteristics, APRETUDE initiation method, PrEP use before initiation on CAB PrEP, service delivery method, and patient subgroups if sufficient data are available.

**Table 10 Definitions of Implementation Outcomes**

[figure not shown]
Implementation Outcomes	Definition	Additional terminology
Acceptability (Proctor, 2011, Weiner, 2017)	Acceptability is the perception among implementation stakeholders that a given treatment, service, practice, or innovation is agreeable, palatable, or satisfactory	meets my approval, seems good, meets my needs, is satisfactory, is appealing, I like, I welcome the use of
		satisfaction with various aspects of the innovation; examples include content, complexity, comfort, delivery, and credibility,
Feasibility (Proctor, 2011, Weiner, 2017)	Feasibility is defined as the extent to which a new treatment, or an innovation, can be successfully used or carried out within a given agency or setting.	practical, realistic, workable, implementable, possible, viable, doable, easy to use, challenging (reverse score)
		Actual fit, suitability for everyday use, convenience*
Utility (Aarons, 2015)	Seen as being useful and helpful in day-to-day operations and in implementing change and EBP	Useful, helpful

\*Convenience is synonymous with published literature terminology and used in this study to measure feasibility

